1.1 Background

1.1.1 Study design

This is a phase 3, multicenter, randomized, double-blind, placebo-controlled, parallel-group study with treatment of QM1114-DP in the LCL and GL, alone or in combination.

Each subject will receive a single treatment of:

- 60 units QM1114-DP (60 units in the LCL and placebo in the GL),
- 50 units QM1114-DP (50 units in the GL and placebo in the LCL),
- 110 units QM1114-DP (60 units in the LCL and 50 units in the GL), or
- Placebo in both the LCL and GL.

Following treatment at baseline, subjects will be monitored for efficacy and safety over a period of approximately 6.5 months.

1.1.2 Number of subjects and randomization

The study will screen approximately 454 male and female adults, 18 years of age and older, with moderate to severe glabellar lines at maximum frown and moderate to severe lateral canthal lines at maximum smile in up to 15 study sites in order to enroll 413 subjects. Following the screening process, eligible subjects will be randomized at the baseline visit (Day 0) in a 2:2:2:1 ratio to:

- 60 units QM1114-DP (60 units in the LCL and placebo in the GL, 118 subjects),
- 50 units QM1114-DP (50 units in the GL and placebo in the LCL, 118 subjects),
- 110 units QM1114-DP (60 units in the LCL and 50 units in the GL, 118 subjects), or
- Placebo in both the LCL and GL (59 subjects).

Randomization will be stratified by study center.

1.2 Study Objectives

The objective of the study is to evaluate the efficacy and safety of a single dose of QM1114-DP for the treatment of moderate to severe LCL and moderate to severe GL, alone or in combination.

1.2.1 Primary efficacy objective

The primary objective of this study as assessed using the endpoints outlined in [Section 1.4.1](#) is to evaluate the efficacy of a single dose of 60 units of QM1114-DP in the LCL and 50 units of QM1114-DP in the GL, alone or in combination, compared to placebo for the treatment of moderate

	Title 43QMI902 Statistical Analysis Plan US - QM1114-DP - GL&LCL	Doc id MA-43265
--	--	----------------------------------

Effective date: 2021-02-05 13:16

Effective

[figure not shown]
Version: 1.0

to severe LCL using the Investigator 4-point Photographic Scale of Lateral Canthal Line Severity (LCL-ILA) (described in [Section 1.3.1](#)) and Subject 4-point Photographic Scale of Lateral Canthal Line Severity (LCL-SLA) (described in [Section 1.3.2](#)) at maximum smile, and for the treatment of GL using the Validated 4-point Photographic Scale of Glabellar Line Severity: Investigator Live Assessment (GL-ILA) (described in [Section 1.3.3](#)) and Static 4-point Categorical Scale of Glabellar Line Severity: Subject Live Assessment (GL-SLA) (described in [Section 1.3.4](#)) at maximum frown, respectively.

1.2.2 Secondary efficacy objectives

The secondary efficacy objective of the study as assessed using the endpoints outlined in [Section 1.4.2](#) is to evaluate the efficacy of a single dose of 60 units of QM1114-DP in the LCL and 50 units of QM1114-DP in the GL, alone or in combination, and placebo for the treatment of moderate to severe LCL and GL using the LCL-ILA and GL-ILA, respectively.

CCI

1.2.4 Safety objective

The safety objective is to evaluate the safety of a single dose of 60 units of QM1114-DP in the LCL and 50 units of QM1114-DP in the GL, alone or in combination, compared to placebo for the treatment of moderate to severe LCL and GL.

1.3 Efficacy assessment

For all assessments, baseline will be defined as the observation that is closest to but prior to study injection on Day 0. Likewise, in general change from baseline (Δ) will be calculated as the value at a given time point, X , minus the baseline value:

$$\Delta = X \text{ Value} - \text{Baseline (Day 0) Value}$$

 GALDERMA	Title 43QMI902 Statistical Analysis Plan US - QMI114-DP - GL&LCL	Doc id MA-43265
--	---	----------------------------------

Effective date: 2021-02-05 13:16

Effective

Version: 1.0

1.3.1 Investigator 4-point Photographic Scale of Lateral Canthal Line Severity (LCL-ILA)

The LCL-ILA is a 4-point validated scale for assessment of lateral canthal lines ([Appendix A](#)). The validated LCL-ILA, developed by Galderma, includes two grading systems: one for the Investigator live assessments at maximum smile, **CCI**

CCI. The scale represents LCL severities from none (grade 0), mild (grade 1), moderate (grade 2), to severe (grade 3). Each grade is also depicted by an individual photograph and descriptive text.

The Investigators will use the LCL-ILA for direct, live comparison with the subject's face at

CCI maximum smile. Left and right LCL should be assessed separately at **CCI**

maximum smile. The Investigator will perform the LCL-ILA at:

- Screening/Baseline (prior to treatment) visit(s)
- all post-treatment visits.

Multiple responder indicators will need to be created as follows:

- For the co-primary LCL endpoint, LCL-ILA indicator: subjects that achieved a score of 0 or 1, and had at least 2 grade improvement from baseline at maximum smile at Month 1, for both left and right LCL, will have the value '1'. This indicator will be used in combination with the primary endpoint LCL-SLA indicator to define the co-primary LCL endpoint composite responder.
- Subjects who achieve a score of 0 or 1 in the LCL-ILA at maximum smile, for both left and right LCL, at each respective post-baseline visit will be considered an LCL-ILA at maximum smile responder for that visit

CCI

- Subjects that achieved at least 1 grade improvement from baseline in the LCL-ILA at maximum smile, for both left and right LCL, at a given post-baseline visit will be considered an LCL-ILA at maximum smile grade 1 improvement responder for that visit.

CCI

- Subjects that achieved at least 2 grade improvement from baseline in the LCL-ILA at maximum smile, for both left and right LCL, at a given post-baseline visit will be considered an LCL-ILA at maximum smile grade 2 improvement responder for that visit.

CCI

1.3.2 Subject 4-point Photographic Scale of Lateral Canthal Line Severity (LCL-SLA)

Similar to the LCL-ILA, the LCL-SLA is also a 4-point validated scale for assessment of LCL ([Appendix B](#)). The validated LCL-SLA, developed by Galderma, includes two grading systems: one for the subject's live assessments at maximum smile, and one for the subject's live assessments **CCI**. The scale represents LCL severities from Level 0, Level 1, Level 2, to Level 3. Each grade is also depicted by an individual photograph and descriptive text.

This assessment will be done independently of the Investigator's assessment. Subjects will be asked to evaluate their LCL at maximum smile **CCI** (left and right side separately) at:

 GALDERMA	Title 43QMI902 Statistical Analysis Plan US - QMI114-DP - GL&LCL	Doc id MA-43265
--	---	----------------------------------

Effective date: 2021-02-05 13:16

Effective date:

Effective

Version: 1.0

- Screening/Baseline (prior to treatment) visit(s)
- all post-treatment visits

Multiple responder indicators will need to be created as follows:

- For the co-primary LCL endpoint, LCL-SLA indicator: subjects that achieved a score of 0 or 1, and had at least 2 grade improvement from baseline at maximum smile at Month 1, for both left and right LCL, will have the value '1'. This indicator will be used in combination with the primary endpoint LCL-ILA indicator to define the co-primary LCL endpoint composite responder.
- Subjects who achieve a score of 0 or 1 in the LCL-SLA at maximum smile, for both left and right LCL, at each respective post-baseline visit will be considered an LCL-SLA at maximum smile responder for that visit

CCI

- Subjects that achieved at least 1 grade improvement from baseline in the LCL-SLA at maximum smile, for both left and right LCL, at a given post-baseline visit will be considered an LCL-SLA at maximum smile grade 1 improvement responder for that visit.

CCI

- Subjects that achieved at least 2 grade improvement from baseline in the LCL-SLA at maximum smile, for both left and right LCL, at a given post-baseline visit will be considered an LCL-SLA at maximum smile grade 2 improvement responder for that visit.

CCI

1.3.3 Validated 4-point Photographic Scale of Glabellar Line Severity: Investigator Live Assessment (GL-ILA)

The GL-ILA is a 4-point validated scale for assessment of glabellar lines. The validated 4-point Photographic Scale of Glabellar Line Severity ([Appendix C](#)) includes two grading systems: one for investigator live assessments at maximum frown, CCI

The scale represents the severity of GL from none (grade 0), mild (grade 1), moderate (grade 2) to severe GL (grade 3) as shown in Table 1.

Table 1. The static 4-point categorical scale.

Grade	Severity of Glabellar Lines	Description
0	No wrinkles	Smooth skin
1	Mild wrinkles	Fairly smooth skin
2	Moderate wrinkles	Frown lines
3	Severe wrinkles	Deep frown lines

The Investigators will use the GL-ILA for direct, live comparison with the subject's face CCI at maximum frown. The Investigator will perform the GL-ILA at:

- Screening/Baseline (prior to treatment) visit(s)

	Title 43QMI902 Statistical Analysis Plan US - QMI114-DP - GL&LCL	Doc id MA-43265
--	---	----------------------------------

Effective date: 2021-02-05 13:16

Effective date:

Effective

Version: 1.0

- all post-treatment visits.

Multiple responder indicators will need to be created as follows:

- For the co-primary GL endpoint, GL-ILA indicator: subjects that achieved a score of 0 or 1, and had at least 2 grade improvement from baseline at maximum frown at Month 1 will have the value '1'. This indicator will be used in combination with the primary endpoint GL-SLA indicator to define the co-primary GL endpoint composite responder.
- Subjects who achieve a score of 0 or 1 in the GL-ILA at maximum frown at each respective post-baseline visit will be considered a GL-ILA at maximum frown responder for that visit

CCI

- Subjects that achieved at least 1 grade improvement from baseline in the GL-ILA at maximum frown at a given post-baseline visit will be considered a GL-ILA at maximum frown grade 1 improvement responder for that visit.

CCI

- Subjects that achieved at least 2 grade improvement from baseline in the GL-ILA at maximum frown at a given post-baseline visit will be considered a GL-ILA at maximum frown grade 2 improvement responder for that visit.

CCI

1.3.4 Static 4-point Categorical Scale of Glabellar Line Severity: Subject Live Assessment (GL-SLA)

Similar to the GL-ILA, subjects will also assess their GL severity using the GL-SLA. The GL-SLA consists of 4 scaled options, presented in Table 1. This assessment will be done independently of the Investigator's assessment. Subjects will be asked to evaluate their GL at maximum frown at:

- Screening/Baseline (prior to treatment) visit(s)
- all post-treatment visits

Multiple responder indicators will need to be created as follows:

- For the co-primary GL endpoint, GL-SLA indicator: subjects that achieved a score of 0 or 1, and had at least 2 grade improvement from baseline at maximum frown at Month 1 will have the value '1'. This indicator will be used in combination with the primary endpoint GL-ILA indicator to define the co-primary GL endpoint composite responder.
- Subjects who achieve a score of 0 or 1 in the GL-SLA at maximum frown at each respective post-baseline visit will be considered a GL-SLA at maximum frown responder for that visit
- Subjects that achieved at least 1 grade improvement from baseline in the GL-SLA at maximum frown at a given post-baseline visit will be considered a GL-SLA at maximum frown grade 1 improvement responder for that visit.
- Subjects that achieved at least 2 grade improvement from baseline in the GL-SLA at maximum frown at a given post-baseline visit will be considered a GL-SLA at maximum frown grade 2 improvement responder for that visit.

 GALDERMA	<small>Title</small> 43QMI902 Statistical Analysis Plan US - QMI114-DP - GL&LCL	<small>Doc id</small> MA-43265
---	--	-----------------------------------

Effective date: 2021-02-05 13:16

Effective

Version: 1.0

CCI

 GALDERMA	<small>Title</small> 43QMI902 Statistical Analysis Plan US - QMI114-DP - GL&LCL	<small>Doc id</small> MA-43265
---	--	-----------------------------------

Effective date: 2021-02-05 13:16

Effective

Version: 1.0

CCI

 GALDERMA	Title 43QMI902 Statistical Analysis Plan US - QMI114-DP - GL&LCL	Doc id MA-43265
--	---	----------------------------------

Effective date: 2021-02-05 13:16

Effective

Version: 1.0

1.4 Efficacy endpoints

1.4.1 Primary efficacy endpoint

There are two primary efficacy endpoints, based on treatment location. The first primary endpoint is the composite responder rate at Month 1 using the GL-ILA and the GL-SLA at maximum frown.

A composite responder is defined as a subject who achieves a score of 0 or 1 in GL severity and at least 2 grades improvement from baseline on both the GL-ILA and GL-SLA scales, concurrently, at Month 1.

The second primary endpoint is the composite responder rate at Month 1 using the LCL-ILA and the LCL-SLA at maximum smile.

A composite responder is defined as a subject who achieves a score of 0 or 1 in LCL severity and at least 2 grades improvement from baseline on both the LCL-ILA and LCL-SLA scales, concurrently, at Month 1 for both left and right sides.

1.4.2 Secondary efficacy endpoints

Secondary endpoints include:

- (i) Percentage of subjects who achieve a score of 0 or 1 at each post-treatment visit using the GL-ILA at maximum frown
- (ii) Percentage of subjects who achieve a score of 0 or 1 at the same visit for both left and right sides summarized for each post-treatment visit using the LCL-ILA at maximum smile

CCI

 GALDERMA	<small>Title</small> 43QMI902 Statistical Analysis Plan US - QMI114-DP - GL&LCL	<small>Doc id</small> MA-43265
---	--	-----------------------------------

Effective date: 2021-02-05 13:16

Effective

Version: 1.0

CCI

 GALDERMA	<small>Title</small> 43QMI902 Statistical Analysis Plan US - QMI114-DP - GL&LCL	<small>Doc id</small> MA-43265
---	--	-----------------------------------

Effective date: 2021-02-05 13:16

Effective

Version: 1.0

[figure not shown]
CCI

Effective date: 2021-02-05 13:16

Effective

Version: 1.0

 GALDERMA	<small>Title</small> 43QMI902 Statistical Analysis Plan US - QMI114-DP - GL&LCL	<small>Doc id</small> MA-43265
---	--	-----------------------------------

1.5 Safety assessments and endpoints

For details regarding the safety assessments, please refer to the Clinical Study Protocol (CSP) Section 7.2.

1.5.1 Adverse events

Adverse events (AEs) are to be monitored throughout the course of the study. All AEs reported will be coded using the Medical Dictionary for Regulatory Activities (MedDRA, version in force at the time of database freeze) and classified by MedDRA preferred term (PT) and system organ class (SOC). AEs will be defined as treatment-emergent adverse events (TEAEs) if the AE had an onset time greater than or equal to the time of study treatment. The study period for the purpose of AE collection is defined as the period from the signing of a study specific informed consent to study exit.

A two-point scale ("Yes" or "No" response) will be used for the causality assessments. The

 GALDERMA	Title 43QMI902 Statistical Analysis Plan US - QM1114-DP - GL&LCL	Doc id MA-43265
--	---	----------------------------------

Effective date: 2021-02-05 13:16

Effective

Version: 1.0

Treating Investigator should be asked to indicate a response to each of the following questions in the electronic Case Report Form (eCRF):

- “Do you consider that there is a reasonable possibility that the event may have been caused by the study product?”
- “Do you consider that there is a reasonable possibility that the event may have been caused by the study product injection procedure?”

If either of these questions is answered with a ‘Yes’, the AE will be considered related.

AE endpoints include incidence and severity of TEAEs.

1.5.2 Laboratory safety tests

Hematology and blood chemistry laboratory tests will be performed at baseline (before treatment) and Month 6. Laboratory safety test endpoints include:

- Values collected at each visit
- Changes from baseline

1.5.3 Focused physical examination

Physical examination will be done at screening/baseline (before treatment), Day 7, Day 14, Month 1 and Month 6. Normal, abnormal and clinically significant findings will be assessed.

1.5.4 Vital signs

Vital signs will be assessed from baseline (before and after treatment), Day 7, Day 14, Month 1, and Month 6. Vital signs endpoints include:

- Values collected at each visit
- Changes from baseline

1.5.5 Neutralizing antibody testing

Blood samples will be taken for measurement of serum neutralizing antibody testing against QM1114-DP at baseline (before treatment), Month 1, and Month 6. Analysis of the blood samples include in vitro screening and confirmatory (if positive screening result) ELISA assays to test for the presence of binding antibodies, and in vivo mouse protection assay (MPA) to test for the presence of neutralizing antibodies. The MPA will only be conducted if the subject has a positive confirmatory result.

1.5.6 Electrocardiogram (ECG)

ECG recordings will be done at baseline (before treatment), Month 1 and Month 6. The following items will be measured:

- RR interval
- PR interval
- QRS interval
- QT interval
- Heart rate (HR)
- QTcB interval
- QTcF interval

 GALDERMA	<small>Title</small> 43QMI902 Statistical Analysis Plan US - QMI114-DP - GL&LCL	<small>Doc id</small> MA-43265
---	--	-----------------------------------

Effective date: 2021-02-05 13:16

Effective

Version: 1.0

During each visit where ECG is conducted, the ECG will be recorded in triplicates. In addition to the individual measurements the above items will be aggregated into a mean value per visit (mean of all beats). ECG endpoints include:

- Aggregated values collected at each visit
- Changes from baseline
- QTcB and QTcF prolongation criteria
- Overall assessment (Normal, Abnormal Not Clinically Significant, Abnormal Clinically Significant) of the ECG

 GALDERMA	Title 43QMI902 Statistical Analysis Plan US - QM1114-DP - GL&LCL	Doc id MA-43265
--	---	----------------------------------

Effective date: 2021-02-05 13:16

Effective

Version: 1.0

2 Statistical Methods

2.1 General methods

All tables, listings, and figures will be programmed using SAS Version 9.4 or higher. Data collected in this study will be documented using summary tables and subject data listings created by using the SAS® system. Confidence intervals (CI) and p-values will be 2-sided and performed at a significance level of 5%, unless otherwise specified. Data for all subjects in the clinical database will be included in the data listings. Calculated (derived) variables will be listed as appropriate. Any changes from the SAP will be detailed in the clinical study report.

All efficacy, safety and baseline characteristics variables will be presented using descriptive statistics within each treatment group, and graphs as appropriate. Continuous variables will be summarized using descriptive statistics (number of observations, mean, standard deviation [SD], median, minimum, and maximum). Categorical variables will be presented in frequency tables with number and percentage of observations for each level. Missing counts for all variables will be presented for informational purposes only and will not be included in percentage calculations.

Study days will be calculated relative to the injection of study drug. Day 0 will be the day of study drug administration. Baseline will be the last assessment prior to the injection of study drug unless otherwise indicated. The Screening Visit 1 (Day -14 to Day 0) will be considered the visit prior to injection of study drug. Because the Screening visit and Baseline visit (Day 0) may be performed on the same day, the Screening visit can also be Day 0.

Adverse events, cosmetic/aesthetic procedures and implant history events, medical history events, and concomitant treatments/procedures will be coded using MedDRA, Version 23.0.

Prior/concomitant medications and procedural anesthetics will be coded using the World Health Organization (WHO) Drug Dictionary Global, 1 Sep 2019 B3 or higher.

In general, efficacy, safety, **CCI** analyses will be performed and summarized by treatment group (QM1114-DP, placebo), unless otherwise stated.

2.1.1 Visit windows

Study visits are expected to occur according to the protocol schedule in [Appendix F](#). All data will be tabulated per the evaluation visit as recorded on the eCRF even if the assessment is outside of the visit window. In data listings, the relative study day (in relation to date of study drug administration) of all dates will be presented. There will not be any windowing for unscheduled visits in the analysis, and unscheduled visits will not be included in any analyses. Unscheduled visits, if any, will be presented in listings only.

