	Screening ¹	Baseline/Day 0 ¹ (within 2 weeks after screening)	Day 7 (±1 day)	Day 14 (± 3 days)	Month 1 (±5 days)	Month 2 (±5 days)	Month 3 (±5 days)	Month 4 (±5 days)	Month 5 (±5 days)	Month 6/ET ² (±5 days)
Informed Consent	X									
Demographic Data ³ including, Fitzpatrick skin type, medical history & concurrent diseases, previous facial treatments/procedures (toxin naïve/non-toxin naïve)	X									
Inclusion /Exclusion Criteria	X	X ⁴								
Concomitant Therapies/ Procedures	X	X	X	X	X	X	X	X	X	X
Adverse Events	X	X ⁵	X	X	X	X	X	X	X	X
Urine Pregnancy Test ⁶	X	X ⁴								X
Vital Signs (blood pressure, heart rate, and respiratory rate) ⁷		X ⁵	X	X	X					X
ECG		X ⁴			X					X
Blood sample clinical chemistry and hematology		X ⁴								X
Blood sample for serum antibody testing		X ⁴			X					X
Lateral Canthal Lines Severity (LCL-ILA)	X	X ⁴	X	X	X	X	X	X	X	X
Glabellar Line Severity (GL-ILA)	X	X ⁴	X	X	X	X	X	X	X	X
Focused Physical Examination (face, head, neck) ⁸	X	X ⁴	X	X	X					X
Photography		X ⁴	X	X	X	X	X	X	X	X
Randomization		X ⁴								
Treatment		X ⁹								
CCI										
Subject assessments										
Lateral Canthal Lines Severity (LCL-SLA) ¹⁰	X	X ⁴	X	X	X	X	X	X	X	X
Glabellar Line Severity (GL-SLA) ¹⁰	X	X ⁴	X	X	X	X	X	X	X	X
CCI										

1. Screening and baseline visits may be on the same day. If completed on the same day, only perform study assessments once (i.e., PE, UPT, SLA, ILA, AE, concomitant therapies/procedures, inclusion/exclusion review)
2. If the subject withdraws before the final visit the assessments at Month 6/ET should be completed, if possible.
3. Includes date of birth, gender, race, ethnicity, height, and weight.
4. To be performed before treatment.
5. To be performed before treatment and post-treatment.
6. Females of childbearing potential.
7. Vital signs are taken seated after 10 minutes rest. Vital signs are taken prior to any blood draw (excluding post-treatment measurements on Day 0).

8. Post-baseline, events suggestive of remote spread of toxin are also considered while doing clinical evaluations based on the subject's symptoms and signs. Directed questioning and examination will then be performed as appropriate.
9. Following treatment administration, subjects will be monitored at the study center for 30 minutes.
10. Subjects will make their Lateral Canthal Line and/or Glabellar Line assessments independently of the Investigator's assessment.

CONFIDENTIAL
Page 20 of 96
Effective

Effective date: 2020-06-09 07:02

Effective

Version: 4.0

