In the early 1990s, patients treated with BoNT-A for blepharospasm were observed to lose their frown lines and,^{5,9} since publishing these observations, the use of BoNT-A in the aesthetic setting has accelerated. Injectable BoNT-A products have been investigated for multiple aesthetic indications in attempts to reverse the appearance of aging, especially in the facial region.² In the treatment of facial lines, the effect of BoNT-A injections usually persists for approximately 4-6 months. Facial muscle activity and severity of the facial wrinkles then returns to baseline. Full functionality of facial muscles is usually restored by approximately 6 months post-treatment.¹⁰

There are four BoNT-A products currently licensed in the United States (US) for the treatment of GL (Botox Cosmetic®, Dysport®, Xeomin® and Jeuveau™), and one licensed for the treatment of LCL (Botox Cosmetic®). QM1114-DP is a novel botulinum toxin type-A1 which is presented as a liquid formulation. Unlike the main commercially available botulinum toxins in the US, QM1114-DP is manufactured and formulated without any animal or human proteins. As a novel BoNT-A with a differentiated formulation, QM1114-DP is being developed for the treatment of moderate to severe GL and LCL in adults over 18 years.

 GALDERMA	<small>Title</small> 43QMI902 Clinical Study Protocol - QM1114 - LCL and GL	<small>Doc id</small> MA-40371
--	---	--

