5.5 Procedures/Reasons for Subject Discontinuation

An Investigator may decide to discontinue a subject from the clinical study for safety reasons.

Although the importance of completing the entire clinical study should be explained to the subject by the clinical study personnel, any subject is free to discontinue participation in this clinical study at any time and for whatever reason, specified or unspecified, and without any prejudice. No constraints are to be imposed on the subject, and when appropriate, a subject may be treated with other conventional therapy when clinically indicated.

When a subject does not complete the clinical study, he/she will be fully assessed, if such assessment is possible. The procedures designated for the Month 6/ ET visit should be completed for all subjects discontinuing the clinical study and the appropriate eCRF should be completed.

All discontinuations and the reason for discontinuation are to be documented by the Investigator on the exit form. For discontinuation due to an AE, the AE form is to be completed. The Investigator should also ensure that the subject receives suitable therapy for the AE.

Potential reasons for discontinuation are listed below:

- Adverse Event: Complete an AE form.

 GALDERMA	Title 43QMI902 Clinical Study Protocol - QM1114 - LCL and GL	Doc id MA-40371
--	---	----------------------------------

Effective date: 2020-06-09 07:02

Effective date:

Effective

Version: 4.0

- Withdrawal by Subject: Includes consent withdrawal, subject relocation, schedule conflicts, etc. Explain the reason for withdrawal in the comment section of the eCRF exit form.
- Lost to Follow-up: Confirmed with two documented phone calls and a certified letter (delivery receipt requested) without answer. Explain in the comment section of the eCRF exit form.
- Other: This category is to be used for a subject who discontinues due to a reason other than as specified in the predefined categories above. Explain the reason for discontinuation in the comment section of the eCRF exit form.

A subject who has been randomized and assigned a kit number/randomization number cannot be replaced by another subject if he/she discontinues the clinical study for any reason. Additional subjects could be enrolled (randomized/assigned to treatment) in order to attain the number of evaluable subjects.

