8.1.7 Month 6/Visit 10 or Early Termination visit (\pm 5 days)

At the Final/ET, the Investigator or designee will:

 GALDERMA	Title 43QMI902 Clinical Study Protocol - QM1114 - LCL and GL	Doc id MA-40371
--	---	----------------------------------

1. Ask the subject about AEs using an open-ended question, such as "Have you noticed any change in your health since the last visit?" Record all events, as appropriate.
2. Ask the subject about any changes in his/her concomitant therapies/procedures (added, removed or changed) since the previous visit. Record all changes.
3. Instruct the subject on how to complete the LCL-SLA at **CCI** maximum smile. Subject to complete self-assessment of bilateral LCL severity using the 4-point Photographic Scale. (Section [7.1.2](#) and [Appendix 2](#))
4. Instruct the subject on how to complete the GL-SLA at maximum frown Subject to complete self-assessment of GL severity using the Static 4-point Categorical Scale. (Section [7.1.4](#))
5. **CCI**
- 6.
- 7.
8. Obtain the subject's vital signs (blood pressure, heart rate, and respiratory rate). Vital signs are to be taken seated after 10 minutes rest (Section [7.2.2](#)).
9. Obtain 12-lead ECG recording after the subject has been resting in a supine position for at least 10 minutes ([Section 7.2.3](#)).
10. Collect blood sample (chemistry and hematology) for analysis at the central laboratory ([Section 7.2.4](#)).
11. Collect blood sample for neutralizing antibody testing ([Section 7.2.5](#)).
12. If the subject is a female of childbearing potential, collect urine for UPT and complete pregnancy test (see laboratory manual for additional procedures). Document the result.
13. Take subject photographs (refer to photo manual for complete instructions). If the subject is wearing make-up, instruct the subject to remove it prior to taking photographs.
14. Investigator to complete assessment of the subject's bilateral LCL severity at **CCI** maximum smile using the 4-point Photographic Scale (LCL-ILA). (Section [7.1.1](#) and [Appendix 1](#))
15. Investigator to complete assessment of the subject's glabellar line severity at **CCI** maximum frown using the 4-point Photographic Scale (GL-ILA). (Section [7.1.3](#) and [Appendix 3](#))
16. Investigator to perform a focused PE. ([Appendix 6](#))
17. Exit the subject from the study.

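### The SAP has no readable rule for early-termination assessments collected at the combined Month 6/ET visit; read literally, they are summarised as Month 6 whatever day they were made

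*SAP*

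**What the plan says.** **Visit assignment.** SAP section 2.1.1 states: "All data will be tabulated per the evaluation visit as recorded on the eCRF even if the assessment is outside of the visit window". Actual timing appears only in listings, where "the relative study day (in relation to date of study drug administration) of all dates will be presented". The same section says that "unscheduled visits will not be included in any analyses".

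**Early termination.** Protocol section 8.1.7 describes one combined visit, "Month 6/Visit 10 or Early Termination visit". Footnote 2 to the protocol's Schedule of Assessments (Table 2) reads: "If the subject withdraws before the final visit the assessments at Month 6/ET should be completed, if possible". Section 5.5 adds: "The procedures designated for the Month 6/ ET visit should be completed for all subjects discontinuing the clinical study". SAP Appendix F, to which section 2.1.1 refers for the visit schedule, repeats the single Month 6/ET column.

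**What uses Visit 10.** SAP section 1.4.2 defines the secondary GL endpoint as "Percentage of subjects who achieve a score of 0 or 1 at each post-treatment visit using the GL-ILA at maximum frown", with a matching LCL-ILA endpoint. Section 2.4.2 analyses these on observed cases, and section 2.1 leaves missing values out of percentages. Section 2.4.4 describes the accompanying CMH analyses as descriptive. The safety sections (1.5 and 2.5) refer to Month 6 without mentioning ET.

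**The concern.** A subject who leaves on, say, Day 56 and attends a final assessment completes the Visit 10 procedures. Section 2.1.1 then directs tabulation by the recorded visit, whatever the day. If that visit is Visit 10, a Day 56 score enters both numerator and denominator of the Month 6 rate.

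Timing matters because the effect is expected to wane. Protocol section 1.1 says that "the effect of BoNT-A injections usually persists for approximately 4-6 months". In an active arm, scores from the first three months and from Month 6 are therefore not interchangeable.

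Three things are exposed:

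- the Month 6 responder rates in the by-visit tables and figures;
- the Month 6 summaries of laboratory tests, ECG, vital signs and physical examination;
- in rare cases, the Month 1 primary endpoint. A score taken at an exit inside the Month 1 window but recorded only under Visit 10 would leave Month 1 empty. The observed value would then be replaced by multiple imputation, or by the baseline score in the BOCF sensitivity analysis.

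**Working it through.** **No stated figure to reproduce.** The documents give no dropout rate, no Month 6 response rate and no response rate at ET. The rise from 350 to 413 subjects protects the size of the mITT population under remote assessment; it is not a dropout allowance.

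**Windows.** Table 2 of the protocol sets one month at 28 days and counts windows from Day 0.

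- Month 1: 28 ± 5 = Day 23 to 33.
- Month 6: 6 × 28 = 168, and 168 ± 5 = Day 163 to 173.

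An ET visit can fall on any day before Month 6.

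**Bias formula.** Let N be the subjects in an arm with a Visit 10 record, k those whose record is an ET assessment, r6 the rate among subjects truly seen at Month 6, and rE the rate at ET.

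Tabulated rate = [(N − k) × r6 + k × rE] / N, so bias = (k / N) × (rE − r6).

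N = 118 is the planned size of an active arm, taking every subject to have one record or the other. k, r6 and rE are assumptions.

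Worked example with k = 6 and r6 = 10%:

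- rE = 80%: (6/118) × (0.80 − 0.10) = 0.036, or +3.6 points.
- rE = 0%: (6/118) × (0 − 0.10) = −0.005, or −0.5 points.

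Bias in percentage points at r6 = 10%:

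| k of 118 | rE = 0% | rE = 50% | rE = 80% |
|---|---|---|---|
| 2 (about 2%) | −0.2 | +0.7 | +1.2 |
| 6 (about 5%) | −0.5 | +2.0 | +3.6 |
| 12 (about 10%) | −1.0 | +4.1 | +7.1 |
| 18 (about 15%) | −1.5 | +6.1 | +10.7 |

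With r6 varied from 5% to 20%, the full range over these values of k and rE is −3.1 to +11.4 points. The bias is zero when rE = r6.

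**Primary endpoint.** The Month 1 route needs three things together: an exit on Day 23 to 33, a completed assessment at that exit, and no Visit 5 record. The documents give no basis for counting such cases.

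**The case against.** The strongest objection is that the eCRF is not among the documents. Section 2.1.1 tabulates by the visit recorded there, and the protocol says which procedures a leaver completes, not which label the record carries. This stands, and it is why the point is limited to what the plan allows. It does not close the gap. If ET has its own label, the SAP does not say whether it is a scheduled visit, an unscheduled one to be dropped, or something else. Parts of the SAP are redacted and could hold a rule for the redacted endpoints, but section 2.1.1 is readable and contains none.

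A reader might infer that early dropouts are counted as Month 6 and inflate late response. The documents do not support that. The first half depends on the unseen label and the second on who leaves. Exit before the effect wanes pushes the active-arm rate up; exit by non-responders pushes it down. A visit that happens only where possible also yields fewer ET records than dropouts.

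A reader might also infer that the primary analysis is compromised. It is not shown to be. Nothing stops a site from recording an exit within the Month 1 window as Visit 5. The primary analysis imputes from treatment, baseline, Day 7 and Day 14; only the BOCF sensitivity analysis substitutes baseline. No early-exit score enters Month 1 by error, and the four-test fixed sequence is untouched.

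Nor is tabulating scheduled visits by nominal label a defect. It is a legitimate prespecified choice; only ET records are left open. The reach is modest: one of eight post-treatment visits, descriptive results, and listings of study day and withdrawal date from which ET records can be traced.

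**Conclusion.** The concern holds in a limited form. The SAP's visit rule and the single Month 6/ET visit, taken together and read literally, place ET assessments from any day in the Month 6 summaries, and nothing readable prevents it. That is more than missing detail, because following the written rule produces the mixture.

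The consequence is possible bias in descriptive Month 6 responder rates, plausibly upward in active arms when exit precedes waning, together with Month 6 safety tables that pool different follow-up times. Confidence is high that the rule is missing and low on the sign and size of its effect. Every percentage-point figure given here rests on assumed values of k, r6 and rE and on ET carrying the Month 6 label. Loss of an observed Month 1 score is a rare secondary possibility. The point merits a correction to the SAP but does not threaten the primary conclusion.

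**What to change.** Add a paragraph to SAP section 2.1.1, before unblinding, so that the rule is not chosen with the results in view.

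- **Efficacy.** Assign each ET assessment by study day to the scheduled visit whose protocol window contains it, and only if that visit has no scheduled record. An ET score on Day 23 to 33 then serves as Month 1 when Visit 5 is absent. Count ET as Month 6 only on Day 163 to 173. Otherwise leave it out of the by-visit tables and list it.
- **One window definition.** Use the protocol windows throughout. Midpoint windows would give about Day 21 to 42 for Month 1 (midpoints of 14 and 28, and of 28 and 56) and Day 154 onward for Month 6 (midpoint of 140 and 168). An ET score on Day 158 would be Month 6 under one scheme and not under the other.
- **Safety.** For laboratory tests, ECG, vital signs and physical examination, show ET values that fall outside the window of a visit scheduled for that test in a separate early-termination row. Moving them to the nearest visit would not work for laboratory tests, whose only scheduled post-baseline point is Month 6/ET.

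The cost is one derived analysis-visit variable, an extra row in the safety tables and slightly fewer Month 6 observations. The change makes the Month 6 rate a true observed-case rate; it does not address what leavers would have scored at Month 6.
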